Successful execution of this study will lay the groundwork for a clinical trial to compare the efficacy of a clot-specific imaging modality (**thrombus body scan or TBS**) that has the potential to be more accurate for the diagnosis of VTE, better able to establish the total clot burden in the body with a single test and more widely applicable to patients with renal failure and lung disease.

III. SUBJECT SELECTION

A total of eighty (80) subjects will be recruited for this study, which will be performed at the Massachusetts General Hospital (MGH). All eighty (80) subjects will be studied with the same protocol: a single injection of ⁶⁴Cu-FBP8 and PET-CT imaging at least three hours after injection at four bed positions, which will provide the imaging data for fresh blood clot at the three locations covering all three specific aims.

Inclusion Criteria:

Each subject must meet the following criteria to be enrolled in the study:

- 18 years of age or older with a clinically significant pulmonary embolus (PE) confirmed by a filling defect in CT angiography (CTA), and
- Subjects must receive the radiotracer injection within 72 hours of their diagnosis.

Exclusion Criteria:

- Subjects < 18 years of age
- Time of expected radiotracer injection > 72 hours from the time of a positive venous duplex ultrasound or CT-angiogram,
- Women subjects of childbearing potential who are pregnant, seeking to become pregnant, or have a positive serum pregnancy (beta-HCG) test,
- Unable to lie flat for 45 minutes as assessed by physical examination and medical history (e.g. back pain, arthritis, dyspnea),
- Weight that exceeds the PET camera table limit (300 kg)
- The subject will not be enrolled in the study if the radiation exposure for research studies during the prior 12 months, combined with the exposure from this study would exceed 50 mSv.
- Due to the radiation exposure from imaging studies, all women of childbearing potential will be required to have a negative serum pregnancy test performed prior to any imaging procedures on the same day (if not already done that day). Patients with a positive serum pregnancy test will be excluded. Breast feeding women will also be excluded.
- A pre-existing condition or use of a medication including vasopressors and tPA (due to its effects on clot) that in the opinion of the investigator may place the subject at a substantially increased risk
- Hemodynamic instability, including requiring escalating doses of vasopressor medication.

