- For subjects admitted to the hospital close to the scheduled time for imaging, which is at least 3 hours after injection, the subject will be escorted (transported) in the wheelchair or stretcher/bed by hospital transport and/or study staff depending on the subject conditions to the PET-CT suite; we will follow the hospital standard procedures for patient transport. The PET-CT technician will submit a patient transport order through Epic. When the PET suite becomes available, the hospital transport team will transport to the PET-CT location. If the subjects need to be monitored during the transport, then one of the study physicians will be present during the transport.
- Subjects coming as outpatient will come to the hospital (Anesthesia or Pulmonary Research area) at least 4 hours prior to the imaging where they will be injected and monitored before taking them to the PET-CT imaging suite.
- Prior to the scan subjects will be asked to urinate to minimize the possibility that they will need to move during the scan.
- The subjects will be positioned on the scanner table; support devices under the back and/or legs will be used as needed to enable the patient to comfortably maintain his/her position throughout the scan.
- A scout image (Topogram) which takes about 10 seconds will be obtained to locate the proper fields for imaging.
- Afterwards, CT and PET scans will be obtained for four bed positions: thorax, pelvis and thighs (2 positions). The CT scan for each position of the PET scans is necessary to correct for the attenuation of the ⁶⁴Cu-FBP8 activity caused by body tissue. We will perform an additional PET/CT scan of the lower portion of the thighs in order to image the full/whole thighs to the knees. Consequently, a total of 4 CT and 4 PET scans will be performed in four different positions. Imaging duration will be less than 10 seconds for each CT, and 10 minutes for each PET scan. The total time of imaging is expected to be approximately 45 minutes.
- We may have to repeat a PET-CT scan if we have an unexpected problem (for example, if subjects need to change position during a scan).
- Subjects will be monitored throughout the imaging session, and measurements including heart rate, blood pressure, and pulse oximetry will be recorded.

Post-scan procedures:

- After the scans are completed and last vital signs collected, the subject will be escorted back to his/her room on the ward if applicable

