Patients will be contacted at 3, 6 and 12 months following the diagnosis of PE. Death and recurrence of DVT-PE will be assessed. Results of any imaging studies (CT angiograms, echocardiograms, or venous duplex ultrasound studies) and serologic studies (follow up d-dimer) will be collected and patients will undergo a survey to collect information about symptoms attributable to PE-DVT as well as quality of life using Standard Form 36,²⁸ VEINES QOL29 and the patient's self-assessment of their overall health status on a 1 – 10 scale, with 1 indicating the worst possible and 10 the best possible health. For patients followed at MGH this will be done in person at the end of their PERT or pulmonary clinic follow up clinic visit. For those followed elsewhere, this will be done by telephone with subjects and their treating physicians. NYHA functional class, 6-min walk distance, and change in pulse oximetry with walking will be assessed.

VI. BIOSTATISTICAL ANALYSIS

Once a patient is enrolled, the subjects will receive an injection of up to 10 mCi ⁶⁴Cu-FBP8 and imaged with CT-PET approximately at least 3 hours after injection, when the “target-to-background” ratio (TBR) of activity is expected to be high based on previous studies.²⁷ With CT-PET the attenuation correction is done using a low-dose CT volumetric scan. Afterwards, PET acquisitions of 10 min duration each are performed in four positions, thorax, pelvis and thighs (2 positions), which are used to assess regional ⁶⁴Cu-FBP8 activity.

Specific data variables:

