The standardized uptake value (SUV) of ⁶⁴Cu-FBP8 uptake in the lungs, pelvis and thighs will be calculated. The target to background ratio (TBR) for ⁶⁴Cu-FBP8 activity will be calculated using as background a region of interest (ROI) created from large cardiac and vascular structures. This corrects the ⁶⁴Cu-FBP8 activity for differences in injected dose and timing of imaging and allows for flexibility in the image timing. One member of our group ([name]) and another from Nuclear Medicine ([name]) will be blinded to the clinical results and will identify the presence or absence of clot in the three imaged locations as well as the anatomic location(s) and extent as best as possible from the overlay of the fibrin activity on the attenuation correction CT scans. Additionally, we will perform quantitative image analyses including the volume of the thrombus ROI, activity of imaged clot in each imaged section and clot burden. The thrombus ROI is defined by a threshold of 50% between peak activity of the ROI and background activity. Multiple ROIs will be used in the case of separated thrombi. Clot burden will be estimated using the sum of ⁶⁴Cu-FBP8 activity within a thrombus ROI and then normalized by the injected dose.

Outcome Measures:

Specific Aim 1: The location and extent of the thrombus region of interest (ROI), its volume and clot burden within the lung ROI will be compared with the ROI of filling defects on CT-angiogram. We will determine the number and location of the thrombus ROI(s) within the lungs, and the overall clot burden as sum of ^{64}Cu -FBP8 activity within a thrombus ROI(s) within the lungs. Additionally, we will calculate the intersection of the thrombus ROI and filling defects ROI relative to volume of the thrombus ROI. That will quantify the fraction of thrombus ROI(s) using a scale from being are completely outside (0) to completely inside (1). Also, we will perform a lung segmentation using the software APOLLO (VIDA Diagnostics) and determine in which lung lobe the thrombus ROI(s) are located.

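### Aim 1's additional PET-CTA overlap index has no tolerance for PET resolution or residual misalignment, so low scores for small emboli cannot be read as uptake outside the filling defect

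*Combined protocol and SAP*

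**What the plan says.** Section VI (Outcome Measures, Specific Aim 1) first compares the location, extent, volume and clot burden of the PET thrombus ROI with the filling-defect ROI on CTA, and counts and locates the PET ROIs. It then adds: "we will calculate the intersection of the thrombus ROI and filling defects ROI relative to volume of the thrombus ROI". The result runs from 0 (wholly outside) to 1 (wholly inside). Lobes are segmented to "determine in which lung lobe the thrombus ROI(s) are located".

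The other relevant statements are:

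- **PET contour** (section VI, Specific data variables): "The thrombus ROI is defined by a threshold of 50% between peak activity of the ROI and background activity".
- **Acquisition** (section V, PET-CT imaging): "Imaging duration will be less than 10 seconds for each CT, and 10 minutes for each PET scan". Gating and breath-hold are not mentioned.
- **CT paired with the PET** (section VI, opening paragraph): "With CT-PET the attenuation correction is done using a low-dose CT volumetric scan". The filling defect is drawn on a different examination, the diagnostic CTA.
- **Timing** (section III): injection within 72 h of diagnosis, and PET at least 3 h after injection.
- **Blinded read** (section VI, Specific data variables): two readers record presence or absence, anatomic location and extent of clot, using PET overlaid on the attenuation-correction CT.

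The text states no PET-to-CTA registration method, tolerance margin, resolution correction, minimum clot size or rule for matching individual clots. It gives no cut-off for the overlap fraction.

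**The concern.** The index credits only the part of the PET contour that falls exactly within the filling defect drawn on CTA. Two things unrelated to probe binding lower it. One is any residual offset between the two examinations. The other is PET blur: for a clot near the scanner's resolution, the 50% contour reflects the resolution and extends beyond the clot.

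Both effects depend on clot size, so an average over ROIs or subjects would partly reflect how large the emboli were. A score near 0 could mean off-target uptake, clot that CTA missed, clot that changed between scans, or a correctly labelled small embolus displaced by a few millimetres. In a proof-of-concept study meant to justify a larger one (section II), these should be distinguishable.

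**Working it through.** The documents give no expected overlap or cut-off, so there is no plan figure to reproduce. The check computes the plan's own index for clots that are, by construction, truly labelled.

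**Inputs from the documents.** Index = volume(PET ROI ∩ CTA ROI) / volume(PET ROI); contour at 50% between peak and background; 10 minutes per PET bed position. The gap from diagnosis to PET can reach 72 + 3 = 75 h or more.

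**Assumed inputs (none is in the documents).** Spherical, uniformly labelled clots of diameter d = 3 to 30 mm; Gaussian PET resolution of 5 or 7 mm FWHM; residual shift t = 0 to 10 mm; no noise. A uniform background cancels, because the threshold lies midway between peak and background.

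**Step 1: misalignment alone.** For two equal spheres, overlap = 1 − 1.5(t/d) + 0.5(t/d)³.

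- t = d/4: 1 − 0.375 + 0.008 = 0.63
- t = d/2: 1 − 0.75 + 0.0625 = 0.31
- t = d: 1 − 1.5 + 0.5 = 0

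This needs no assumption about the scanner.

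**Step 2: blur and shift together.** Each sphere was placed on a 0.5 mm grid, blurred and contoured at 50% of peak. The contour was then intersected with the true sphere shifted by t. Ranges cover FWHM 5 and 7 mm.

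| Clot diameter | No shift | 2 mm shift | 5 mm shift | 10 mm shift |
|---|---|---|---|---|
| 3 mm | 0.08-0.20 | 0.08-0.14 | 0 | 0 |
| 5 mm | 0.29-0.64 | 0.26-0.37 | 0-0.03 | 0 |
| 8 mm | 0.84-1.00 | 0.59-0.71 | 0.18 | 0 |
| 12 mm | 1.00 | 0.87 | 0.45 | 0.02 |
| 20 mm | 1.00 | 0.90-0.94 | 0.67-0.70 | 0.32-0.33 |

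Cross-check: for a 5 mm clot at 7 mm FWHM, the PET contour encloses 3.42 times the clot volume. With no shift the score should be 1/3.42 = 0.29, as found.

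**Step 3: breathing.** Adding 10 mm FWHM of cranio-caudal blur (also assumed) with no shift gives 0.17-0.33 at 5 mm, 0.55-0.73 at 8 mm and 0.91-0.94 at 12 mm.

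**Step 4: shape.** A clot 5 mm wide and 20 mm long scores 0.01-0.07 with a 5 mm shift across its axis, but 0.39-0.61 with the same shift along it.

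**Step 5: would a margin help?** A dilated CTA sphere contains the whole PET contour when t + r(PET) ≤ d/2 + m, where m is the margin. For the 5 mm clot, r(PET) = 2.5 × 1.53^(1/3) = 2.88 mm at 5 mm FWHM and 2.5 × 3.42^(1/3) = 3.77 mm at 7 mm FWHM. With t = 2 mm, m must be at least 2 + 2.88 − 2.5 = 2.4 mm and 2 + 3.77 − 2.5 = 3.3 mm respectively. Under these assumptions, a margin of a few millimetres restores the score to 1.

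**The case against.** The strongest reply has four parts.

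**Role of the index.** It is an additional measure. Location, extent and number of ROIs, and the blinded presence/absence read, would still credit a small displaced clot. A reader might infer that Aim 1 rests on overlap, or that true detections would push Aim 1 towards failure. The documents do not support that: no success criterion, test or cut-off is attached to the fraction, and 0 and 1 are defined as positions, not as false or true detection. This stands. What remains is that no other PET-CTA agreement statistic is defined for the lung, so the overlap is the number most likely to be quoted.

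**Registration.** Most of the loss comes from misalignment, and computing an intersection presupposes a common frame. Silence does not mean that registration will be omitted. This also stands: at a 2 mm residual shift, clots of 12 mm or more score at least 0.87. But registration does not rescue a 5 mm clot (0.26-0.37), so the missing tolerance is a separate gap.

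**Blur.** It might be inferred that blur alone drives scores to near 0. Without respiratory blur it does so only at about 3 mm; at 5 mm it leaves 0.29-0.64.

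**Detectability.** Very small clots may never be contoured. With a = (d/2)/σ and σ = FWHM/2.3548, the retained peak contrast is erf(a/√2) − √(2/π)·a·exp(−a²/2). For a 5 mm clot this is 0.29 at 5 mm FWHM (a = 1.18) and 0.13 at 7 mm FWHM (a = 0.84). Entry requires a clinically significant embolus and the documents give no clot-size distribution, so the affected share is unknown.

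**Conclusion.** The point holds for small emboli. As defined, the index understates spatial agreement for truly labelled clots of about 8 mm or less even after good registration (2 mm residual), and for clots of about 12 mm when the residual is 5 mm (0.45). Emboli of 20 mm or more keep about 0.67 or better at a 5 mm shift. Low scores for small emboli therefore cannot be taken as uptake outside the filling defect.

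The direction follows from geometry. The sizes rest on assumed resolution, shift, clot shape and diameter, and on the clot being visible at all. Real lysis or migration between CTA and PET would also lower the score, and the index cannot separate that from misalignment. The documents do not support a claim that Aim 1 as a whole is biased or that its other comparisons fail. This is a cheap improvement to an additional measure.

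**What to change.** 1. State that the CTA will be registered to the attenuation-correction CT, name the method, and report the residual error.
2. Report the overlap twice, against the filling-defect ROI as drawn and against that ROI dilated by a fixed margin set before analysis to cover PET resolution and residual motion. Show both by clot size.
3. Using the lobe segmentation already planned, add a per-lobe table of PET clot (yes/no) against CTA filling defect (yes/no), with clustering by subject and a separate category for central arteries outside the lobes. Every subject has a CTA-confirmed embolus, so lobes without a filling defect supply the CTA-negative units that a subject-level lung comparison lacks.

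The lobe table should stand alongside the extent measures and not replace them, because Aim 1 asks about extent as well as presence and location.

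The cost is a few sentences in section VI and modest extra analysis of images already acquired, with no new scans. The dilated and lobe-level measures are spatially coarser, and dilation will also credit some off-target uptake close to a clot. That is why the overlap as drawn should be kept beside them.

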Sources of research material will include a) results of history and physical examination, b) medical record review (EPIC, Epic Systems, Verona, Wisconsin, USA) for pertinent clinical and laboratory results, and c) review of clinically relevant imaging studies including CT-angiograms, venous ultrasound with Doppler, echocardiograms, and drug and/or mechanical treatment for VTE. In the case of women of childbearing potential, a serum sample will be collected for the purposes of determining pregnancy status. The data will be used only for research purposes and will be kept anonymous (by using a number without names) and confidential. In addition to PET-CT data acquired as above,

Study Events

PRE-IMAGING			IMAGING			Follow up			
Events	Pre-dosing	Dosing (at least 3 hours before imaging)	CTs	PET		3 months	6 months	12 months	
PERT or Radiology Notifications	X								
Eligibility checklist	X								
Informed consent	X								
Medical History	X								
Physical exam	X								
Vital Signs ^a	X								
IV placement	X								
Pregnancy Test ^b	X								
D-dimer	X								
⁶⁴ Cu-FBP8 injection		X							
PET-CT			X	X					

Hemodynamic measures ^c	X	X	X	X					
ECG ^f	X	X							
Adverse events	X	X	X	X					
VEINES -QOL	X					X	X	X	
6 MWT ^g	X					X	X	X	
EMR Review	X					X	X	X	

- a. Vital signs: respiratory rate, pulse, blood pressure, and temperature.
- b. Pregnancy serum HCG test: Women of childbearing potential.
- c. Hemodynamic measures: During the scan heart rate, respiration rate, heart rhythm, pulse oximetry will be measured. Values will be recorded before probe injection, immediately after probe injection and throughout the scan.
- d. Blood draws: If not done for clinical purposes, blood will be drawn prior to radiotracer injection - blood will be sent for a coagulation panel [Fibrinogen, PTT (PTT, ARPT), PT/INR (INR/ARINR)], platelets and D-dimer.
- e. Anticoagulants used as well as timing and dosing will be recorded.
- f. ECG: All subjects will have ECGs for monitoring before and after the scans if available.

Follow up:

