Specific Aim 2: The thrombus ROI, its volume and clot burden within the thigh ROI will be compared with the location and extent of the clot on venous duplex ultrasound. We will determine the number and location of the thrombus ROI(s) within the thigh ROI, and the overall clot burden as sum of ^{64}Cu -FBP8 activity within a thrombus ROI(s) within the thigh ROI. Additionally, we will quantify the volumes and locations of the thrombus ROIs of the PET scan and the venous duplex ultrasound relative to each other. Also, we will perform a vessel segmentation using the 3D Slicer (open source software) and determine the location of thrombus ROI(s) with the blood vessel.

Specific Aim 3: The prevalence of high ^{64}Cu -FBP8 fibrin activity in the pelvic ROI and upper extremity ROI's will be reported. Additionally, as a secondary analysis, both the total fibrin activity in the imaged fields, excluding the liver, gallbladder, kidneys and urinary bladder normalized by injected dose for all patients will be correlated with the plasma D-dimer drawn at the time of imaging. D-dimer levels will be drawn daily from the time of first diagnostic imaging to the fibrin probe imaging (up to 3 days maximum in total) as well as PT, PTT, platelets and fibrinogen. Anticoagulants used, as well as timing and dose will be carefully recorded during this period.

For all Specific Aims, death, VTE recurrence, and quality of life measures will be compared with the clot burden measured by PET and conventional imaging modalities, stratified by treatment (systemic thrombolysis, catheter thrombolysis, or heparin alone) using multiple correlation, ANOVA, and t-tests for pairwise comparisons.

VII. RISKS AND DISCOMFORTS

^{64}Cu -FBP8 PET probe:

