for identification of incidental findings. If incidental findings are identified and the subject gives consent, we will provide this information to the subject's primary care physician. If clot is identified by the fibrin scan in places not seen or not evaluated by the treating team (e.g. the pelvis), this information will be conveyed to the treating team and appropriate clinically-approved testing can be done to assess this if the treating team deems it necessary.

Venous thromboembolism (VTE), comprising deep venous thrombosis and pulmonary embolism, is a major public health problem. The estimated average annual incidence rate of overall VTE among persons of European ancestry ranges from 104 to 183 per 100,000 person-years and is similar to that of stroke,¹ the fifth leading cause of death in 2013.² Incidence rates for PE±DVT are 29 to 78 per 100,000 person-years and for leg DVT alone are 45 to 117 per 100,000 person-years.¹ For those of African descent, the incidence may be higher.³⁻⁵ Over the decade from 2002 to 2012, the incidence of VTE has been rising.⁶ This has raised the question of whether this rise represents a true increase in incidence or potentially over diagnosis with more available imaging techniques. Whatever the reason, it is clear from this data that it is vitally important to improve the accuracy of identifying VTE with targeted diagnostics. The knowledge gained from this study will allow an assessment of whether or not a fibrin-specific PET probe has the potential to improve our diagnostic accuracy of VTE, diagnose VTE in previously difficult areas (pelvis) and broaden the patient population on which specific diagnostic testing can be performed, such as those with renal failure.

IX. MONITORING AND QUALITY ASSURANCE

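### Does Aim 2 need to say which leg ultrasound the thigh PET is compared with, and what happens to subjects without one?

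*Combined protocol and SAP*

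**What the plan says.** - **Comparison.** Section II, Aim 2, sets PET against conventional imaging for whether DVT is there, where it lies and how far it extends, and names leg venous Doppler ultrasound as the test by which DVT is diagnosed. Section VI, Specific Aim 2, says the PET thrombus region, its volume and its clot burden "will be compared with the location and extent of the clot on venous duplex ultrasound".
- **PET side.** Section III: "All eighty (80) subjects will be studied with the same protocol". Section VI: two readers blinded to the clinical results "will identify the presence or absence of clot in the three imaged locations".
- **Ultrasound side.** Entry under Section III needs a CT-confirmed PE, not an ultrasound. The Study Events table in Section V has no ultrasound row. The data come from "review of clinically relevant imaging studies including CT-angiograms, venous ultrasound with Doppler", and Section V records duplex results only where they exist. Duplex scans done during the 12-month follow-up are collected too.
- **Timing.** Section III excludes subjects whose injection would fall more than 72 hours "from the time of a positive venous duplex ultrasound or CT-angiogram". Section IV starts the same 72-hour clock at the first diagnostic imaging. By contrast, Aim 3 fixes its comparator: total fibrin activity is "correlated with the plasma D-dimer drawn at the time of imaging".
- **Disclosure.** Section VIII says of clot found by PET: "in places not seen or not evaluated by the treating team (e.g. the pelvis), this information will be conveyed to the treating team", which may then order tests.

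**The concern.** Three things are unstated: which examination is the comparator when a subject has several, how old a negative one may be (the 72-hour rule names only a positive one), and what is done with subjects who have none. Aim 2 is the only aim so placed. The CT angiogram of Aim 1 is fixed by the entry rule, and the D-dimer of Aim 3 by its timing.

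The disclosure rule adds a possible bias. A PET-positive thigh that was never scanned may be scanned because of PET; a PET-negative one will not be. If such scans counted, PET-positive subjects would be verified more often. A prompted first scan can add a subject who is PET-positive and ultrasound-negative, but never one who is PET-negative and ultrasound-positive. A prompted repeat scan that turns positive works the other way. The direction is therefore unknown, and the result is meant to prepare a larger trial.

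**Working it through.** The plan states no figure for Aim 2 and no calculation behind the 80 subjects, so there is nothing to reproduce. All rates below are assumptions. Subjects are counted, not legs, and DVT status means what ultrasound shows or would show.

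**1. Prompted first scans.** Let v be the share with a routine ultrasound and q the share of unscanned PET-positive subjects scanned because of PET. Verification is v for PET-negative subjects and v + (1 − v)q for PET-positive ones. The ratio of PET+/US− to PET−/US+ counts is multiplied by 1 + q(1 − v)/v, whatever the sensitivity, specificity or prevalence:

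| v | q = 0.2 | q = 0.5 | q = 0.8 |
|---|---|---|---|
| 0.5 | 1.20 | 1.50 | 1.80 |
| 0.7 | 1.09 | 1.21 | 1.34 |
| 0.9 | 1.02 | 1.06 | 1.09 |

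Repeat scans act in the opposite direction. If a share r of PET+/US− subjects turns positive, the factor is 1 − r, for example 0.75 at r = 0.25.

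**2. High-end example.** Take 80 subjects, 40% with DVT, sensitivity 0.70, specificity 0.90. The full table is 22.4 PET+/US+, 9.6 PET−/US+, 4.8 PET+/US− and 43.2 PET−/US−.

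- Routine scans only (v = 0.5, q = 0): PET+/US− is 4.8 × 0.5 = 2.4 and PET−/US+ is 9.6 × 0.5 = 4.8. There are 40 evaluable subjects and agreement is 82%.
- Prompted scans admitted (q = 0.8): PET-positive verification is 0.5 + 0.5 × 0.8 = 0.9. PET+/US− is 4.8 × 0.9 = 4.32 and PET−/US+ stays at 4.8. There are 20.16 + 4.8 + 4.32 + 21.6 = 50.9 evaluable subjects, and agreement is 41.76/50.88 = 82%.
- The proportions within each ultrasound group move more. PET-positive among US-negative goes from 10% to 4.32/25.92 = 17%. PET-negative among US-positive goes from 30% to 4.8/24.96 = 19%.

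**3. Which scan the text points to.** The shift in step 2 arises only if prompted scans enter Aim 2, and no sentence brings them in. Section II speaks of DVT as diagnosed by ultrasound. Sections III and IV count time from the diagnostic imaging. Later duplex scans appear under Follow up, next to recurrence. Section VIII describes possible benefit, and its one example is the pelvis, which is not the Aim 2 region. With the diagnostic scan as comparator, q = 0 and the factor is exactly 1.

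**4. Subjects without a scan.** If they were counted as ultrasound-negative, with 30% DVT, sensitivity 0.80, specificity 0.90 and 75% coverage, apparent specificity would be (0.63 + 0.015)/(0.645 + 0.13) = 0.832; at 50% coverage it would be 0.66/0.85 = 0.776. But Aim 2 compares location and extent on two images. A subject with one image has nothing to compare, so leaving that subject out is the ordinary course.

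**5. Would a written rule gain anything?** A cut-off at disclosure of the PET finding seems natural, but disclosure follows only certain positive findings. Suppose 20% of otherwise unscanned subjects have a routine scan after PET, and that for PET-positive subjects it falls after disclosure. At v = 0.5, PET-negative verification becomes 0.5 + 0.5 × 0.2 = 0.6 against 0.5, a ratio factor of 0.5/0.6 = 0.83 (0.7/0.76 = 0.92 at v = 0.7). In the example the within-group proportions become 2.4/28.32 = 8.5% and 5.76/16.96 = 34%. That rule brings in its own imbalance. A cut-off common to everyone, such as tracer injection, avoids it, but largely restates the diagnostic-scan reading.

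No wording removes selection by clinical ordering. With routine ultrasound in 70% of subjects with DVT and 40% of those without, the count ratio is multiplied by 0.40/0.70 = 0.57. The within-group proportions stay at 10% and 30% unless ordering also depends on clot size or symptoms.

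**The case for a change.** The strongest case for a change is that the omission is certain and the remedy is a few words. No text chooses among several scans, limits the age of a negative one, or deals with missing ones, so two analysts could reach different answers from the same data. The steady 82% agreement is no comfort: in the same example apparent sensitivity moves from 0.70 to 20.16/24.96 = 0.81 and specificity from 0.90 to 21.6/25.92 = 0.83. Blinding the PET readers does not help, because the issue is who receives an ultrasound. An unscanned thigh also fits the Section VIII wording, since the pelvis is given only as an example.

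What stands is that the text is silent on all three points, and that prompted scans, if admitted, could shift the within-group proportions noticeably when routine coverage is low. What does not stand is the step from silence to a faulty analysis. The larger shifts need low routine coverage, frequent prompting of thigh scans, and an analyst who admits scans that the plan does not assign to Aim 2. The missing-as-negative figures need an analyst to score an examination that was never done. Section VI also lists only descriptive quantities for Aim 2 (number, location, volume, burden, relative position), with no sensitivity, specificity, test or success threshold that such a shift could overturn.

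**Conclusion.** No change is needed. This is a gap in wording that an analyst fills sensibly: use the diagnostic leg ultrasound of the current episode in subjects who have one, report how many do not, and keep follow-up and prompted scans apart. On that reading the prompted-scan effect is nil.

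The alternative is bounded only by assumption: a ratio factor from 1.02 (90% routine coverage, 20% prompting) to 1.80 (50% coverage, 80% prompting), about two subjects of 80 at the high end, with repeat scans pulling the other way. Coverage, prevalence and prompting rates are not in the document, so no actual distortion is shown. The conclusion rests on reading Sections II to IV as pointing to the diagnostic scan, and on Aim 2 being a descriptive part of a proof-of-concept study. Selection through clinically ordered ultrasound remains either way, and belongs in the discussion of the results.
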